4.4. Sample Size Calculation

The sample size calculation has been performed with the assumption that the results of this study will be similar to those obtained in scientific literature with the same device which is around 98% (Oliva 2010).

The chosen statistical test and sample size equation for this clinical study is:

Formula:

$$n = P * (1 - P) * (\frac{Z_{1-\alpha} + Z_{1-\beta/2}}{|P - P_0| - \delta})^2$$

Source: The-Medical-Device-Sample-Size-Cookbook.pdf

Z values taken from this source.

The inputs required for this calculation are defined below

The inputs required for this calculation are defined below					
VARIABLE	VALUE	CLARIFICATION			
n	?	the sample size			
Р	2% (0,02)	This is called the True Proportion, i.e. the proportion to be tested. We assume that 2% of implants will fail to integrate.			
P0	3% (0,03)	This is called the Null Hypothesis Proportion. It's the reference value (gold standard) we are testing up against, and thus not assumed but originating from the literature			
P - P0	1% (0,01)	The minimum clinically meaningful effect, i.e. the difference between the two proportions - which makes it interesting to test for equivalence.interesting to test.			
δ (Delta)	8% (0,08)	The testing margin, if the difference in failures is 6% or more, it's not considered equivalent from a clinical perspective.			
H₀ (Null Hypothesis)	P - P ₀ ≥ δ	The difference between the two proportions is 6% or higher. This would mean that it's not equivalent.			

H ₁ (Alt.Hypothesi s)	P - P ₀ < δ	The difference between the two proportions is less than 6%, and thus equivalent.
α (Alpha)	5% (0,05)	The recommended minimum standard (can be lower)
Power (1 - β)	80% (β = 0,20)	The recommended minimum standard (can be higher)

The inputs in the formula are:

$$n = 0.02 * (1 - 0.02) * ((1.645 + 1.282) / ((0.02 - 0.03) - 0.08))^2 = 20.729 >> 21$$

This is, that we would need at least 21 subjects to illustrate equivalence of results of this clinical study versus the previous CeraRoot study (PMCF #191220). For this reason the estimated sample size of 200 patients for the present study PMCF 200806 is more than sufficient based on this statistical calculation.

5. Scientific Background

5.1. References:

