3.2. H₁ (Alt. Hypothesis)

There are significant differences between the failure rate in this study and the failures rate in the literature.

3.3. Study Type:

Observational [Patient Registry]

3.4. Observational Study Model:

Cohort

3.5. Time Perspective:

Prospective

3.6. Biospecimen Retention:

None Retained

NCT: 04598776 Protocol PMCF #200806 3 / 7

3.7. Biospecimen Description:

3.8. Enrollment:

200 [Anticipated/ predicted]

175 real participants enrolled in the study.

3.9. Number of Groups/Cohorts:

1

3.10. Target Follow-Up Duration:

3 Years

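### The sample-size table labels 1 point clinically meaningful but treats differences up to 6 or 8 points as equivalent, and the design can only test an upper limit

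*Protocol*

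**What the plan says.** Protocol section 4.4 (Sample Size Calculation) tabulates the inputs of a one-sample equivalence formula for a proportion.

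- **True proportion P, 2%:** "We assume that 2% of implants will fail to integrate".
- **Reference proportion P0, 3%:** described as coming from the literature.
- **P - P0, 1%:** "The minimum clinically meaningful effect, i.e. the difference between the two proportions".
- **Margin δ, 8% in the value column:** "The testing margin, if the difference in failures is 6% or more, it's not considered equivalent from a clinical perspective".
- **Alternative hypothesis:** "The difference between the two proportions is less than 6%, and thus equivalent".

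The null-hypothesis row also uses 6% in words, while the worked calculation puts in 0.08. The section concludes that "we would need at least 21 subjects to illustrate equivalence" with the previous CeraRoot study. Section 3.8 gives the enrolment as "175 real participants enrolled in the study", against 200 anticipated. Section 4.4 gives no reason for the size of the margin relative to the 3% reference.

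**The concern.** An equivalence margin should not exceed the smallest difference that matters clinically. If 1 point already matters, a 6- or 8-point difference cannot be clinically equivalent, yet adjacent rows of the table say both.

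The margin is also large relative to the reference rate. With a 3% reference, subtracting 6 or 8 points gives a negative failure rate, so the lower side of any equivalence region is met before a patient is seen. Only the upper side carries information.

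The stake is the meaning of the main conclusion. Implant survival is the primary outcome, and section 4.4 fixes the rule by which the result is called equivalent to the previous study. Under that rule a failure rate well above the reference can receive that label.

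**Working it through.** **Inputs (section 4.4 unless stated).** P = 0.02; P0 = 0.03; δ = 0.08 (value column and calculation) or 0.06 (wording of three rows); α = 0.05 with z = 1.645; z for 1 - β/2 = 1.282; n = 175 (section 3.8).

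**1. The plan's own figure.** As substituted in the protocol, with P - P0 signed:

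n = 0.02 × 0.98 × ((1.645 + 1.282) / (-0.01 - 0.08))² = 0.0196 × (2.927 / 0.09)² = 20.73, rounded up to 21.

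The stated 21 is reproduced. The formula as printed takes the absolute difference, so the denominator is 0.01 - 0.08 = -0.07 and n = 34.27, rounded up to 35. At δ = 0.06 it gives 67.17, rounded up to 68. The enrolled 175 exceeds all of these, so the point here is what the test means, not whether the sample is large enough.

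**2. What the 1% is.** |P - P0| = |0.02 - 0.03| = 0.01. It is the difference between two assumed inputs, and the formula uses it in that role. Nothing in the section derives it as a clinical threshold. Taken at its label, it is exceeded by the margin 0.06 / 0.01 = 6 times or 0.08 / 0.01 = 8 times.

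**3. The region called equivalent.**

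| δ | P0 - δ | P0 + δ | (P0 + δ) / P0 |
|---|---|---|---|
| 6% | -3% | 9% | 3.0 |
| 8% | -5% | 11% | 3.7 |

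A failure rate cannot be negative, so the lower limit never binds.

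**4. What passes with 175 units.** Assume independent units and an exact one-sided 5% binomial test. The largest passing count is the largest r with P(X ≤ r | n = 175, p = P0 + δ) ≤ 0.05.

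| δ | Limit | Largest passing count | Observed rate | P(pass) at true 5% | P(pass) at true 2% |
|---|---|---|---|---|---|
| 6% | 9% | 9 | 9/175 = 5.1% | 0.62 | 0.997 |
| 8% | 11% | 12 | 12/175 = 6.9% | 0.90 | > 0.999 |

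A true rate of 5% is 2.5 times the assumed 2% and 1.7 times the 3% reference (5/3). It would more likely than not be called equivalent under either margin.

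**The case against.** **The 1% row may be only a slip of labelling.** This stands. The figure is arithmetically the assumed difference, so the ratios of 6 and 8 do not prove that a considered clinical threshold was breached. Once the row is relabelled, though, the section contains no statement of what matters clinically apart from the margin itself, which is unexplained.

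**The hypotheses may already be one-sided.** The H0 and H1 rows print a signed P - P0, which has no lower bound. The absolute value in the formula and the word equivalence point the other way, and symbols may have been lost in the table. On the signed reading no decision changes, but the test is then plainly non-inferiority and the word equivalent is still wrong.

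**A reader might infer that a failure rate near 11% would be accepted as equivalent to 3%.** The documents do not support that. 11% is the boundary for the true rate, and only at δ = 8%; under the 6% wording it is 9%. With 175 units a true rate of 11% passes only 4.5% of the time, and no observed rate above 6.9% passes.

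**A reader might also want a tighter margin matched to the 175 enrolled.** The document gives no clinical basis for one. The study period ended in 2023 and this version is dated July 2024, so a margin fitted to the achieved enrolment would have no better justification than the present one.

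**Independence is an assumption.** Section 4.4 defines failure per implant, section 3.8 counts participants, and section 3.13 admits patients with several missing teeth. The pass probabilities would change with more than one implant per patient and with clustering. The label conflict and the negative lower limit do not depend on this.

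**Conclusion.** The point holds. As written, section 4.4 calls a 1-point difference clinically meaningful and treats differences up to 6 points (8 in the calculation) as clinically equivalent. The likelier error is the label on the 1% row. Independently of that label, the lower limit is negative, so the study can conclude only that the failure rate is below 9% or 11%, not that it is equivalent to 3%.

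Under independence, with 175 units and an exact one-sided 5% test, results up to 5.1% or 6.9% observed failures would pass, and a true 5% rate would pass with probability about 0.62 or 0.90. The adequacy of the sample size against the plan's own formula is not in question, and no particular replacement margin follows from the document. The 6% versus 8% conflict is a separate error; it matters here because it leaves the limit undefined.

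**What to change.** - Relabel the 1% row as the assumed true difference between P and P0.
- State the hypotheses as one-sided non-inferiority: H0, failure rate at or above P0 + δ; H1, failure rate below P0 + δ. Use one reconciled δ throughout the table and calculation.
- Justify that δ against the 3% reference, and say openly when the justification was written.
- Replace the word equivalent, in the table and in the closing paragraph of section 4.4, with the conclusion that the failure rate is below the stated limit.
- Report the one-sided 95% upper limit of the failure rate, so that readers can judge the result whatever margin is kept. State the unit of analysis (implant or patient) and allow for several implants in one patient if the unit is the implant.

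The cost is protocol wording and a somewhat less favourable claim. No further patients or data are needed.

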3.1. H₀ (Null Hypothesis)

There are no significant differences between the failure rate in this study and the failures rates in literature regarding this dental implant.

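### Section 4.4 gives two equivalence margins, 8% and 6%, and its minimum of 21 subjects does not follow from its own printed formula

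*Protocol*

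**What the plan says.** Section 4.4 of the protocol introduces its content with "The chosen statistical test and sample size equation for this clinical study is", so it serves as the statement of the test as well as of the sample size. Its table and worked line give:

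- **Delta, value:** 8% (0,08).
- **Delta, explanation in the same row:** the result is not equivalent "if the difference in failures is 6% or more".
- **H0:** written in symbols against delta, then explained as "The difference between the two proportions is 6% or higher".
- **H1:** written in symbols against delta, then explained as "The difference between the two proportions is less than 6%, and thus equivalent".
- **Formula:** the denominator is printed as |P − P0| − δ, and the table lists P − P0 as 1% (0,01), a positive number.
- **Worked line:** ends in "0.02 - 0.03) - 0.08))^2 = 20.729 >> 21", which uses the signed difference and 0.08.
- **Conclusion:** "we would need at least 21 subjects to illustrate equivalence of results of this clinical study".

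Sections 3.1 and 3.2 state hypotheses of another kind. The null is "There are no significant differences between the failure rate in this study and the failures rates in literature regarding this dental implant" and the alternative is "There are significant differences between the failure rate in this study and the failures rate in the literature". Neither names a margin.

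**The concern.** The margin decides whether the study may claim equivalence, and section 4.4 gives it two values. The 6% figure appears three times in words, while 8% is the only value assigned to the symbol and the only one used in the arithmetic. H0 and H1 are defined by that symbol and then explained with the other figure, so each of those rows contradicts itself. Some results would be equivalent under one line of the table and not under another.

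Sections 3.1 and 3.2 do not settle it. They have no margin, and they make absence of a difference the null, whereas in section 4.4 the null is non-equivalence.

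The stated minimum sample size also depends on a substitution that differs from the printed formula. Timing adds to the need for clarity: this version is dated 21/07/2024 and the title gives the study period as 2020–2023. Nothing in the text shows that the margin was changed.

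**Working it through.** **Inputs (all from section 4.4):** P = 0.02, P0 = 0.03, δ = 0.08 or 0.06, z-values 1.645 and 1.282. Enrolment of 175 is from section 3.8.

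**Failure-rate limits.** Upper: 0.03 + 0.08 = 0.11, or 0.03 + 0.06 = 0.09. Lower: 0.03 − 0.08 = −0.05, or 0.03 − 0.06 = −0.03. A rate cannot be negative, so only the upper limit can bind.

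**Sample size.** n = P(1 − P) × ((1.645 + 1.282)/D)² = 0.0196 × 2.927²/D² = 0.16792/D².

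| Denominator D | δ | n | Rounded up |
|---|---|---|---|
| signed: −0.01 − 0.08 = −0.09 | 8% | 20.73 | 21 (the protocol's figure) |
| as printed: 0.01 − 0.08 = −0.07 | 8% | 34.27 | 35 |
| signed: −0.01 − 0.06 = −0.07 | 6% | 34.27 | 35 |
| as printed: 0.01 − 0.06 = −0.05 | 6% | 67.17 | 68 |

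The protocol's 20.729 against 20.731 here is rounding. The figure of 21 needs both δ = 0.08 and the signed difference.

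**Effect on the conclusion (illustration).** The protocol does not state the following, so they are assumptions: one implant per patient, N = 175, and equivalence declared when a one-sided 95% upper limit lies below 11% or 9%. Three versions of the rule are compared.

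| Rule | Most failures passing at 6% | Most failures passing at 8% | Discordant counts |
|---|---|---|---|
| Exact (Clopper-Pearson) | 9 (limit 8.80%) | 12 (10.87%) | 10–12 |
| Wald | 10 (8.60%) | 13 (10.69%) | 11–13 |
| Point estimate only | 15 (8.57%) | 19 (10.86%) | 16–19 |

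Probability of a discordant result, from the binomial distribution with N = 175:

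| True failure rate | Exact | Wald | Point estimate |
|---|---|---|---|
| 2% | 0.3% | 0.09% | <0.001% |
| 3% | 3.7% | 1.6% | 0.01% |
| 6% | 36% | 31% | 5.8% |

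At the planned 2%, the probability of passing at 6% and at 8% is 0.9970 and 0.9999 (exact), 0.9991 and 1.0000 (Wald), and 1.0000 for both (point estimate).

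If 6% is intended but 8% is applied, the exact rule declares equivalence at a true 9% failure rate with probability P(X ≤ 12) = 19.8% instead of P(X ≤ 9) = 4.2%, against the stated alpha of 5%.

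**The case against.** The strongest reply concerns the second error. Only the upper limit can bind, and the distance from the planned 2% to 11% is 0.09, which is what the signed substitution uses. The absolute value uses 0.07, the distance to a lower limit of −5% that can never be reached. On that view, 21 suits the real one-sided question and only the printed formula is at fault.

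This does not rescue the figure. The formula has the bars and a β/2 term, and the table gives the difference as +1%. A signed one-sided calculation with the power term at 1 − β (z = 0.842) would give 14.96 at 8%, so 15 rather than 21. And 21 is too few under an exact one-sided 95% limit: with no failures at all, the upper limit is 1 − 0.05^(1/21) = 13.3%, above 11%.

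A related point stands. The values 35 and 68 are the printed formula evaluated, not validated minimum sizes. Under the exact rule, 35 subjects at the 8% margin pass only with no failures, which at a true 2% has probability 0.98^35 = 49%, not the stated 80% power. At 68 subjects and 6%, up to 2 failures pass, with power 84%.

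It is also fair that the large discordance figures need true failure rates of 6% or 9%, far above the planned 2%. They rest on assumed rules too: the eligibility criteria allow multiple teeth per patient, so the number of implants may exceed 175. The analysis plan, not available here, may fix the decision rule. None of this removes two values for the margin within one table, and a plan that refers to the protocol's margin would inherit both.

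**Conclusion.** The point holds and must be fixed. The equivalence margin is given as both 8% and 6%, so the failure-rate limit is 11% or 9%, and no passage reconciles them. The stated minimum of 21 subjects is not what the printed formula yields under either margin. Both conclusions come directly from section 4.4 and need no outside assumption.

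The practical effect is small. Enrolment of 175 is well above 35 and 68, so by this formula the study is not too small. At the planned failure rate a conflict between the margins has a probability of about 0.3% at most among the three rules tried. It becomes material only if the true rate is well above plan. Those probabilities depend on the illustrative assumptions of one implant per patient, N = 175 and a one-sided 95% limit. The seriousness lies in an unresolved decision threshold, in a version dated after the study period, and not in any expected loss of power.

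**What to change.** - State one margin, with its justification, and use it in the delta row, H0, H1 and the calculation. State the resulting failure-rate limit (11% or 9%).
- Make formula and substitution agree. As printed, n = 0.02 × 0.98 × (2.927/(0.01 − δ))², which is 35 for δ = 0.08 and 68 for δ = 0.06. Present this as the result of that formula and correct the concluding sentence on the minimum number.
- Rewrite sections 3.1 and 3.2 so that they carry the equivalence hypotheses of section 4.4, with non-equivalence as the null.
- Add a dated sentence on when the margin was set. If that cannot be documented, report the conclusion under both margins.

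The cost is text edits in two sections, one recalculated number and either a dated sentence or one extra result line. No patients are added. The downside is a larger stated minimum and possibly a stricter threshold.

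### Section 4.4 drops the absolute value from its own formula: the minimum is 35 (8% margin) or 68 (6% margin), not 21, though the enrolled sample still suffices

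*Protocol*

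**What the plan says.** All of the calculation is in Protocol section 4.4. The printed formula is n = P(1 − P) × [(Z(1−α) + Z(1−β/2)) / (|P − P0| − δ)]². The input table gives P = 0.02, P0 = 0.03, a difference of 0.01 entered as a positive number, δ = 0.08, α = 0.05 and power 80%.

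The worked line substitutes "1.645 + 1.282) / ((0.02 - 0.03) - 0.08))^2 = 20.729 >> 21". The protocol concludes that "we would need at least 21 subjects to illustrate equivalence of results of this clinical study" and that the planned 200 patients "is more than sufficient based on this statistical calculation". Section 3.8 reports "175 real participants enrolled in the study".

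Two other features of the table bear on the result:

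- **Margin.** The value column has δ at 8%, but its explanation reads "The testing margin, if the difference in failures is 6% or more, it's not considered equivalent from a clinical perspective". The null row reads "The difference between the two proportions is 6% or higher" and the alternative row "The difference between the two proportions is less than 6%, and thus equivalent".
- **Unit.** P is a proportion of implants ("We assume that 2% of implants will fail to integrate"), while n is reported in subjects. Section 3.13 admits patients with more than one tooth to replace.

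**The concern.** With P below P0, the signed difference is −0.01, and subtracting δ moves the denominator away from zero instead of towards it. The distance used becomes 0.09 where the printed formula gives 0.07. Because n varies with the inverse square of that distance, the required number is understated.

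The figure of 21, with its 80% power, is the only stated ground for calling the sample adequate. If it is wrong, the justification in the protocol is wrong even where the conclusion is right, and the number could be carried into a report or a later study as a minimum that supports an equivalence claim.

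**Working it through.** **Inputs (section 4.4).** P = 0.02, so P(1 − P) = 0.0196; P0 = 0.03; z values 1.645 and 1.282, sum 2.927; δ = 0.08 (value column) or 0.06 (explanation and hypothesis rows).

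**1. The plan's figure.** Signed difference, δ = 0.08: denominator −0.01 − 0.08 = −0.09.

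0.0196 × (2.927 / 0.09)² = 20.73 → 21. The stated figure is reproduced.

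**2. The formula as printed.** |P − P0| = 0.01.

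| δ | Denominator | n | Rounded up |
|---|---|---|---|
| 0.08 | −0.07 | 0.0196 × (2.927/0.07)² = 34.27 | 35 |
| 0.06 | −0.05 | 0.0196 × (2.927/0.05)² = 67.17 | 68 |

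**3. Could 21 be a one-sided calculation?** A one-sided test would justify the signed difference, but it would use z(1−β) = 0.842 in place of 1.282, with sum 2.487.

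- δ = 0.08: 0.0196 × (2.487/0.09)² = 14.97 → 15
- δ = 0.06: 0.0196 × (2.487/0.07)² = 24.74 → 25

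Neither gives 21. The worked line pairs a one-sided distance with a two-sided z value.

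**4. Normal-approximation power at n = 21.** SE = √(0.0196/21) = 0.03055. The upper limit P0 + δ lies δ + 0.01 above P, and the lower limit P0 − δ lies δ − 0.01 below it.

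- Upper limit alone: Φ(0.09/SE − 1.645) = 0.903 at 8%; Φ(0.07/SE − 1.645) = 0.741 at 6%.
- Both limits: 0.903 + Φ(0.07/SE − 1.645) − 1 = 0.903 + 0.741 − 1 = 0.644 at 8%; 0.741 + Φ(0.05/SE − 1.645) − 1 = 0.741 + 0.497 − 1 = 0.238 at 6%.

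The lower limits are 3% − 8% = −5% and 3% − 6% = −3%. No failure rate can fall below them, so the two-limit figures describe the formula more than any real risk. The upper limit is the one that matters.

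**5. Exact binomial check on the upper limit.** One-sided 5% test against P0 + δ (11% or 9%), true rate 2%. The normal approximation is poor here, because the expected number of failures in 21 is only 21 × 0.02 = 0.42.

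- n = 21: the best possible result, no failures, has an upper limit of 1 − 0.05^(1/21) = 13.3%. This exceeds both 11% and 9%, so no outcome passes and power is zero at either margin.

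| Margin | n | Failures allowed | Exact power |
|---|---|---|---|
| 8% (against 11%) | 35 | 0 | 0.98³⁵ = 49% |
| 8% | 55 | 1 | 70% |
| 8% | 56 | 2 | 90% |
| 8% | 175 | 12 | 99.99% |
| 6% (against 9%) | 68 | 2 | 84% |
| 6% | 83 | 2 | 77% |
| 6% | 84 | 3 | 91% |
| 6% | 175 | 9 | 99.7% |

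At 8%, exact power is at least 80% for every n from 56 (checked to 399). At 6% it first reaches 80% at 68, dips below for some larger n because the count is discrete, and stays above 80% from 84 (checked to 399).

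**The case against.** The strongest defence is that the hypothesis rows in the table are written without absolute bars, as a difference at or above δ against one below it. On that reading only an excess of failures matters, the relevant distance is from 2% up to P0 + δ, and at 8% that distance is exactly the 0.09 in the worked line. The normal approximation then gives 90% power at n = 21, better than the 80% claimed, and the one-sided minimum would be 15, so 21 would err on the safe side. The move from 21 to 35 also comes from the distance to a negative lower limit that cannot be crossed.

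Part of this stands. The section may conflict with itself on whether the test is one- or two-sided, although bars in the table could have been lost when the PDF was read. The 64% and 24% two-limit powers should not be read as the real shortfall. But the defence does not recover 21: a consistent one-sided calculation gives 15 or 25, and 21 falls short of 25 at the 6% margin. The 90% is an artefact of the approximation, since the exact test cannot pass at 21 under either margin.

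A second objection is that 35 is itself a weak minimum, with 49% exact power. That is correct. It is the right output of the printed formula, not a number on which adequacy should rest.

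A third is that nothing in the study changes, because enrolment is already counted. That also stands, and it is why the point is minor.

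**Conclusion.** The error holds and is minor. The minimum of 21 is not what the plan's formula and inputs give; the formula gives 35 at an 8% margin or 68 at 6%. So 21 is too low by 14 (14/35 = 40%) or 47 (47/68 = 69%). No single corrected figure can be given until δ is reconciled.

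The conclusion on adequacy survives: 175 and 200 exceed 68, and also the exact thresholds of 56 and 84. Exact power at 175 is above 99% at either margin. This rests on the protocol's own assumptions of a true failure rate of 2% and a reference of 3%, and on n counting independent units. Several implants in one patient would weaken the last assumption, and the protocol gives no figure from which to size that effect.

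**What to change.** In section 4.4:

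1. Reconcile δ across the value column, its explanation and both hypothesis rows, and make the hypothesis rows agree with the formula on whether the absolute difference is tested.
2. Correct the worked line to |0.02 − 0.03| − δ and replace 21 with the matching result, 35 at 8% or 68 at 6%, labelled as the output of the normal-approximation formula.
3. Do not rest adequacy on that figure. Add one sentence giving exact binomial power at the 175 enrolled: 99.99% at 8% (up to 12 failures) or 99.7% at 6% (up to 9 failures), for independent units.
4. State n in the same unit as P: either patients with any failed implant, or implants with an allowance for several in one patient.

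The cost is a rewording of one section. No patients are added and the conclusion that the sample suffices stays.

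### The stated minimum of 21 subjects does not have the stated 5% alpha and 80% power: at about 0.4 expected failures, an exact test on 21 subjects cannot show equivalence at all

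*Protocol*

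**What the plan says.** Section 4.4 presents one normal-approximation equation as both the test and the sample size method. Its inputs are:

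- True failure proportion P = 0.02: "We assume that 2% of implants will fail to integrate".
- Reference P0 = 0.03, treated as a fixed value: "It's the reference value (gold standard) we are testing up against".
- Margin delta = 0.08 in the value column. The explanation beside it uses another figure: "if the difference in failures is 6% or more, it's not considered equivalent from a clinical perspective". Both hypothesis rows also use 6%.
- Alpha 5% and power 80%.

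The worked line ends "1.645 + 1.282) / ((0.02 - 0.03) - 0.08))^2 = 20.729 >> 21". The section concludes that "we would need at least 21 subjects to illustrate equivalence" and that "the estimated sample size of 200 patients for the present study PMCF 200806 is more than sufficient". Section 3.8 gives 200 as the anticipated enrolment and then reports "175 real participants enrolled in the study".

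The section mentions neither an exact method nor the small expected number of failures.

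**The concern.** The formula relies on the observed failure proportion being roughly normal. With a 2% event rate and about 20 subjects, the most likely result is no failure at all, and the approximation has nothing to work on. The stated minimum may then have neither the stated alpha nor the stated power.

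The worked line also drops the absolute value in the printed formula. A sponsor who corrected only that slip would publish a second figure from the same approximation, so the approximation needs its own check.

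At stake is the justification of the sample size, because the protocol calls 200 patients "more than sufficient based on this statistical calculation". If a normal-approximation interval of the Wald type were carried into the analysis, the error rate of the equivalence conclusion would be affected too.

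**Working it through.** **Inputs (Section 4.4).** P = 0.02, P0 = 0.03, alpha = 0.05 one-sided (z = 1.645), z for power = 1.282. The upper equivalence limit is P0 + delta: 0.11 with delta 0.08, or 0.09 with delta 0.06. The lower limit, P0 - delta, is below zero under either margin and cannot bind.

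**1. The protocol's figure.** 0.02 × 0.98 × (2.927 / (-0.09))² = 0.0196 × 1057.7 = 20.73, rounded up to 21. This reproduces the stated result apart from the third decimal.

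**2. The formula as printed.** With the absolute value, the denominator is 0.01 - 0.08 = -0.07, and n = 0.0196 × (2.927 / 0.07)² = 34.27, rounded up to 35. With delta 0.06 it is -0.05, and n = 67.17, rounded up to 68.

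**3. What 21 subjects can show.** Expected failures are 21 × 0.02 = 0.42. The best possible outcome is zero failures.

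- Exact upper limit at 0/21: 1 - 0.05^(1/21) = 13.3%, above both 11% and 9%.
- Exact p-values at 0/21: 0.89^21 = 0.0865 and 0.91^21 = 0.138. Neither is at or below 0.05, so no outcome rejects and power is 0%.
- Score test at 0/21: z = -0.11 / √(0.11 × 0.89 / 21) = -1.61, or -0.09 / √(0.09 × 0.91 / 21) = -1.44. Neither is below -1.645, so power is again 0%.
- Wald rule (estimate + 1.645 × its standard error, compared with the limit): at zero failures the standard error is zero, so 0/21 passes, and it is the only outcome that does. Power is 0.98^21 = 65%. Type I error is 0.89^21 = 8.7% or 0.91^21 = 13.8%.

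**4. What 35 subjects can show (limit 11%).** Zero failures rejects (0.89^35 = 0.017). One failure does not: the exact p is 0.090 and the upper limit is 12.9%. Exact power is 0.98^35 = 49.3%. It is the same for the 9% limit, where 0.91^35 = 0.037 and again only zero failures pass.

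**5. Sizes that deliver 80% with an exact one-sided 5% test at P = 0.02.**

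| Limit | n | Most failures allowed | Exact type I error | Exact power |
|---|---|---|---|---|
| 11% | 55 | 1 | 1.3% | 69.9% |
| 11% | 56 | 2 | 4.6% | 89.8% |
| 9% | 68 | 2 | 4.9% | 84.5% |
| 9% | 78 | 2 | 2.4% | 79.5% |
| 9% | 84 | 3 | 4.9% | 91.2% |

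For the 11% limit, power stays at or above 80% from 56 on. For the 9% limit, 68 is the first size to reach it, power dips below at 77 to 83, and it stays at or above 80% from 84.

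**6. The 175 enrolled.**

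| Limit | Rule | Most failures allowed | Type I error | Power |
|---|---|---|---|---|
| 11% | exact, score | 12 | 4.5% | 99.99% |
| 11% | Wald | 13 | 7.7% | above 99.99% |
| 9% | exact, score | 9 | 4.2% | 99.7% |
| 9% | Wald | 10 | 7.7% | 99.9% |

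Expected failures at 175 are 175 × 0.02 = 3.5.

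**The case against.** The strongest objection is that nothing practical depends on 21. The protocol planned 200 and enrolled 175, and both exceed every size in the working. On the plan's assumptions the claim of sufficiency is true, although the calculation offered for it is not. This stands, and it limits the point to a wrong statement that is cheap to correct.

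A reader might infer that the error rate of the primary conclusion is wrong even at 175. The document does not support that. The 7.7% belongs to a Wald rule, and Section 4.4 prints a sample size equation without naming a Wald interval or any other decision rule. The P(1 - P) variance makes Wald a plausible reading, but a score test is a normal approximation too, and at 175 it has the same cut-offs as the exact test. The analysis method may also be set out in a statistical analysis plan that is not at hand.

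A reader might also take 200 against 175 as a contradiction. It is not: Section 3.8 labels 200 as anticipated and 175 as actual.

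Two further objections stand in part. With the 6% margin and the absolute value kept, the formula gives 68, where exact power is 84.5%, so the approximation does not fail for every input. And 84 rather than 68 is a choice of convention: it applies only if power must hold at every larger size. A mid-p test would reject at 0/21 with the 11% limit (0.0865 / 2 = 0.043), but it does not guarantee the 5% level; here its true type I error would be 8.7%.

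**Conclusion.** The point holds for the stated minimum. Twenty-one subjects give 0% power under exact and score tests with either margin, and 65% power with 8.7% or 13.8% type I error under a Wald rule. None of the three gives 80% power at 5%. Correcting the sign alone gives 35 with the 8% margin, and exact power of 49%.

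The point does not extend to the adequacy of the study: exact power at 175 is at least 99.7% with either margin. The correction is worth making because the sufficiency statement rests explicitly on this calculation.

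The figures assume a true failure rate of 2%, a fixed reference of 3% and independent units. Section 4.4 defines failure per implant and counts n in subjects; clustering of several implants in one patient is not allowed for here.

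**What to change.** In Section 4.4:

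1. Reconcile the margin (8% in the value column, 6% in the explanation and hypotheses). No single replacement for 21 can be given until this is done.
2. Replace 21 with an exact-binomial size: 56 for 8%. For 6%, give 68 as the first size to reach 80%, or 84 if power is to stay at or above 80% for every larger size, and state which convention is used.
3. Base the sufficiency statement on exact power at the 175 enrolled: 99.99% for 8% or 99.7% for 6%, treating units as independent.
4. State that the failure rate is tested by comparing a one-sided exact binomial 95% upper limit with P0 + delta. This rules out a Wald rule, which would have 7.7% type I error at 175.

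The cost is wording and one standard calculation. The exact limit is slightly less favourable than a Wald limit, allowing one failure fewer at 175 (12 against 13, or 9 against 10). No more patients are needed.
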